5.2.2. Features of the sham meditation intervention (control condition)

We adopted a sham meditation practice aimed at being indistinguishable from meditation practice for newcomers (Zeidan et al., 2021). Ensuring the sham's structural equivalence was a pivotal consideration, with meticulous attention to matching the quantity and timing of instructions found in the mindfulness intervention. We underscored non-specific elements of meditation, like a soothing instructor's voice and terminology designed to create the expectation of authentic mindfulness meditation for those unfamiliar with the practice.

However, the instructions deliberately excluded the training of the two fundamental cognitive/meta-cognitive processes crucial in mindfulness practice. This intentional omission involved 1) removing any attentional stability by providing participants with no specific point to anchor their attention and 2) offering no guidance on cultivating mindful meta-cognitive qualities of attention. Participants in the mindfulness group were taught to observe and accept their present-moment experience without judgment or reaction. In contrast, sham instructions offered no such guidance.

5.3 Study measurements

All questionnaires used in this study will be administered via a Qualtrics survey.

5.3.1 One-time measurement (start of the trial)

The following psychological and self-reported assessments will be taken at baseline. Participants will be starting the survey at home in a quiet place.

Neuroticism subscale of the IPIP (IPIP-20; Goldberg et al., 2006) - 5 NEO

domains. The scale consists of 20 items to assess the self-reported levels of neuroticism. Examples of items are "I often feel blue" or "I am filled with doubts about things" (answered on a five-point scale ranging from 1 = Very inaccurate to 5 = Very accurate).

Resilience Scale 14 (RS-14; Mirošević et al., 2019)

The RS-14 is a brief version of the Resilience Scale, comprising 14 items. Each item is rated on a 7-point Likert scale, ranging from 1 to 7. Examples of items are "I usually manage one way or another" or "I am determined". Higher resilience scores are associated with improved mental health, enhanced quality of life, and reduced levels of anxiety and depression.

Demographics Participants will provide demographic information, including age, gender, ethnicity, type of smartphone used for the experiment, as well as its operating system (iOS or Android) and version.

5.3.2 Pre and post measurements

The Five Facet Mindfulness Questionnaire – Short Form (FFMQ-SF; Bohlmeijer et al. 2011). The scale is recommended for comparing pre and post interventions that employ mindfulness training. The scale measures 5 different components; *Observing*; the ability to notice and pay attention to the thoughts, feelings, and surroundings. *Describing*; the attitude to express the experiences in words, to describe thoughts and emotions. *Acting with Awareness*; How well they can act with intention and full awareness in their daily activities, rather than on autopilot. *Non-judging of Inner Experience*; tendency to avoid judging their thoughts and emotions as good or bad. *Non-reactivity to Inner Experience*; tendency to experience thoughts and emotions without reacting impulsively. However, recent hierarchical confirmatory factor analysis indicates a preference for a four-factor FFMQ (excluding the 'observe' subscale) in non-meditative samples, as opposed to the traditional five-factor score (Gu et al., 2016). Consequently, the analysis will focus on four facets: Describing,

acting with awareness, non-judging, and non-reactivity. Examples of items are "I can describe my feelings well" or "I can easily talk about my thoughts and opinions" (answered on a five-point scale ranging from 1 = never or very rarely to 5 = Very often or always true). We will take this assessment at baseline and at the end of the experiment.

Repeated measurements (day 1, day 2, day 3)

State Trait Anxiety Inventory (STAI-6; Marteau TM, Bekker) The STAI-6 is a validated short-form version of the 40-item State-Trait Anxiety Inventory (STAI), consisting of 6 items that measure current anxiety symptoms using a 4-point Likert scale. Example items include statements such as "I feel calm" and "I am tense." The STAI-6 will be administered twice daily: once before and once after listening to each audio track.

Ecological Momentary Assessment – (EMA) Participants will indicate their current state on a 7-point Likert scale, with the options "Very Bad," "Bad," "Fairly Bad," "Same as Before," "Fairly Good," "Good," and "Very Good," encoded as [1, 2, 3, 4, 5, 6, 7], respectively. The following questions will be posed to assess various psychological and physical states:

- "Right now, I feel mentally sharp" – to assess perceived cognitive ability.
- "Right now, I feel fatigued" – to assess fatigue and exhaustion.
- "Right now, I feel stressed" – to assess stress levels.
- "Right now, I feel nervous" – to assess nervousness and tension.
- "Right now, I feel depressed" – to assess depressive symptoms.
- "Right now, I am in a good mood" – to assess positive affect and joy.
- "I slept well last night" – to assess subjective sleep quality.

Ecological Momentary Assessment (EMA) will be conducted twice daily, immediately following each administration of the STAI-6 questionnaires.

Heart Rate Variability. To assess parasympathetic activation, participants' heart rate variability (HRV) will be analyzed. HRV is widely recognized as a sensitive marker of stress, regulated by the autonomic nervous system in response to stressors (Goldberger et al., 2001). Participants will monitor their HRV using the 'Camera Heart Rate Variability' smartphone app, which employs Photoplethysmogram (PPG) technology. Notably, smartphone apps utilizing PPG for heart rate measurement have shown consistency with validated methods such as electrocardiography (ECG) in adult populations during resting states (Gudeo-Fernández et al., 2020).

Participants will assess their HRV values seven times over the course of the trial (from Day 1 to Day 3). Participants will be instructed to place their index finger over the smartphone's camera and flash, ensuring both are fully covered. They will hold their finger in place for one minute to allow the device to record their heart rate variability (HRV). Upon completion, the HRV measurement will be saved in the app's local folder. If the finger placement is inadequate, resulting in poor assessment quality, the app will indicate that the CSV file has not been created. In such cases, participants will be asked to repeat the assessment up to two more times. If they are still unable to obtain a valid measurement after the third attempt, they will be instructed to proceed to the next section of the survey.

Participants will then send the corresponding CSV file via email to the study coordinator using a feature included in the app, following the instructions provided at the beginning of the experiment. To ensure that HRV data is not lost, participants will also self-report the corresponding values in the Qualtrics survey.

The first HRV measurement will serve as testing purposes and will be taken immediately after the survey that will prompt participants to go to a quiet place just after the start of the experiment. The additional HRV measurements will be taken twice daily, immediately following the completion of each Ecological Momentary Assessment (EMA).

One-time measurement (end of the trial)

Usability of the intervention to assess the usability of the current pilot trial, a set of questions will be asked to assess the participants' experiences with the mindfulness and sham meditation tracks in terms of ease of use, clarity of instructions, relevance to daily life, engagement levels, comfort, perceived efficacy, willingness to continue usage, any technical issues encountered, and suggestions for improvement.

Perceived Awareness of the Research Hypothesis (PARH; Rubin 2016) is a four-item quantitative self-report tool designed to assess the possible impact of demand characteristics in research settings. Its purpose is to assist in challenging the notion that observed effects can be attributed to demand characteristics. Participants provide their responses to these statements using a 7-point Likert-type scale, where the options range from strongly disagree (1) to strongly agree (7). Examples of statements include: "I was aware of the researchers' objectives in this study" and "I was uncertain about the researchers' intentions in conducting this research".

Expectancy and credibility of the intervention

To assess expectancy, we will use a single item adapted from the Credibility/Expectancy Questionnaire (Devilly & Borkovec, 2000) during the final phase of post-intervention testing: "On a scale from 0 to 10, How effective do you believe the meditation training has been in alleviating stress? (0 = Not at all successful, 10 = Extremely successful)."

To evaluate credibility, participants will respond to a two-part question: "If you were informed that you might have received either meditation training or control training, which type do you believe you received? (Meditation, Control)". "How confident are you in your answer? (0 = Not at all confident, 10 = Extremely confident)".

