The Qualtrics link contains the written informed consent form and the actual experiment. Participants will be able to review all relevant information about the study and either accept or decline to participate. If they do not provide consent, they will be opted out of the study. If consent is provided, participants will proceed to the second screening, which involves answering additional questions about their use of concomitant medication. If they meet the criteria for this stage, they will proceed to answer questions about any neurological or psychiatric conditions. If any of the screening criteria are not satisfied at any point, the study will automatically terminate. Once consent and second screening are complete, participants will then be instructed to move to a quiet environment where they will not be disturbed for the next 35 minutes. They will be asked to download the 'Camera Heart Rate Variability' app and take an initial HRV measurement for testing purposes. Participants will then submit the generated CSV file to the study coordinator via WhatsApp and self-report their rMSSD values in the Qualtrics survey. Participants are instructed to label their CSV files using their anonymous identifier provided by the study coordinator via WhatsApp at the start. Afterward, they will complete a series of questionnaires, including the 20-item IPIP scale, the RS-14, the FFMQ, and various demographic questions such as age, gender, ethnicity, smartphone type used during the experiment, and its operating system (iOS or Android) and version. Pre-intervention assessments of STAI-6, EMA will also be conducted. They will then use the 'Camera Heart Rate Variability' app to measure HRV, submit the generated CSV file to the study coordinator, and self-report their rMSSD values in the Qualtrics survey, as outlined in the instructions.

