8. SAMPLE SIZE AND STATISTICAL METHODS

8.1. Determination of Sample Size.

Since this is a pilot trial, we aim to recruit 60 participants to account for a ~20% dropout rate, ensuring we meet our target of at least 50 participants.

8.2. Statistical analyses.

Our confirmatory statistical analyses will include:

- Bayesian mixed-effects models to investigate the longitudinal changes in self-reported stress measured via STAI-6. The model will have STAI-6 as the

dependent variable, with 'Group' (mindfulness intervention or control), 'Day' (1 to 3), and their interaction term as independent variables. Participant ID will be used as a random intercept to control for individual differences. A BF10 greater than 1 will indicate slightly positive evidence supporting the effectiveness of the mindfulness condition over the control condition in stress reduction.

We will also conduct the following exploratory statistical analyses:

- A Bayesian mixed-effects model to assess longitudinal changes in HRV, using HRV as the dependent variable and 'Group', 'Day' (1 to 3), and their interaction as independent variables. Participant ID will again serve as a random intercept. A BF10 greater than 1 will suggest positive evidence for the mindfulness intervention's effectiveness compared to the control.
- An additional Bayesian mixed-effects model will analyze longitudinal changes in HRV, with the dependent variable being HRV (calculated by the difference in pre- and post-meditation HRV scores) and independent variables including 'Group', 'Day' (1 to 3), and their interaction. Participant ID will account for individual variability in baseline HRV levels.
- Correlational analyses to explore the relationship between changes in mindfulness scores and stress levels, as well as between HRV changes and stress levels.
- Descriptive statistics to summarize baseline participant characteristics, such as neuroticism, RS-14 scores, FFMQ scores related to mindfulness training, and demographic details.
- Analysis of responses regarding the intervention's credibility and participant awareness of the research hypothesis to assess equal credibility of the intervention for the mindfulness condition and the sham.

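### The EMA answer options do not fit the EMA items: four of the seven can be answered in opposite directions, and the midpoint records change on a scale meant for level

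*Combined protocol and SAP*

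**What the plan says.** Section 5.3.2, under the repeated measurements, asks participants to report their present state on a "7-point Likert scale, with the options 'Very Bad,' 'Bad,' 'Fairly Bad,' 'Same as Before,' 'Fairly Good,' 'Good,' and 'Very Good". The codes run from 1 to 7 in that order, so *Same as Before* is 4. The same options serve all seven items.

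- Six items are first-person statements about the present moment, for example "Right now, I feel stressed", included "to assess stress levels".
- The seventh is "I slept well last night".

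On timing, the section states: "Ecological Momentary Assessment (EMA) will be conducted twice daily, immediately following each administration of the STAI-6 questionnaires". The first EMA falls before the Day 1 track; section 5.4 says "Pre-intervention assessments of STAI-6, EMA will also be conducted".

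Neither section says which end of the scale is favourable for a given item, whether any item is reverse-coded, or what *Before* refers to.

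In section 8.2 the confirmatory model concerns "longitudinal changes in self-reported stress measured via STAI-6". No analysis there names the EMA. The exploratory correlations relate mindfulness and HRV changes to stress levels without naming the instrument.

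**The concern.** The items are statements, which call for an answer on agreement, accuracy or intensity. The options offered are ratings of good and bad. For a positively worded item (mentally sharp, good mood, slept well) this does little harm, because endorsing the statement and reporting a good state point the same way. For fatigued, stressed, nervous and depressed they point in opposite directions. A very stressed respondent may choose the lowest option because the state is bad, or the highest because the statement fits well.

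The midpoint is a separate fault and does not depend on how direction is read. It asks whether anything has changed, while its neighbours ask about level. A person who is steadily bad or steadily good can truthfully choose it and be coded as neutral.

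Three things are at stake: the EMA data themselves, the exploratory correlations if their stress measure is the EMA item, and the survey method that section 2 wants this pilot to refine for a larger study.

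**Working it through.** The plan gives no figure to reproduce here. The check is a count of items and occasions, plus simple arithmetic on the codes.

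**Inputs (sections 5.3.2, 5.4 and 8.1).** Seven items; two EMAs a day; three days; codes 1 to 7; a target of at least 50 participants after dropout.

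**Exposure to opposite readings.**
- Answers per participant: 7 × 2 × 3 = 42.
- Negatively worded items: 4 (fatigued, stressed, nervous, depressed). Answers on them: 4 × 2 × 3 = 24, and 24/42 = 57%.
- At 50 participants: 50 × 24 = 1,200 of 50 × 42 = 2,100 answers.

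These are answers open to misreading, not a count of errors.

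**Size of a reversal.** A code x under one reading becomes 8 − x under the other. The largest gap is 7 − 1 = 6 points, the full range of the scale.

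**Is the endorsement reading realistic?** Earlier in the Day 1 session the neuroticism items, which are also first-person statements, are "answered on a five-point scale ranging from 1 = Very inaccurate to 5 = Very accurate". Every EMA also directly follows STAI-6, which is again made up of first-person statements. Respondents have therefore just been judging how well statements describe them. The numeric coding suggests that higher means better, but no instruction in the plan tells them so.

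**Effect on an arm difference (illustration only).** Suppose a share q of respondents reverses the scale, equally in both arms and regardless of their true level. A true difference d on a negatively worded item then becomes (1 − q)d − qd = (1 − 2q)d. The documents give no q, so a range is shown:

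| q (assumed) | Share of d retained |
|---|---|
| 0 | 100% |
| 0.1 | 80% |
| 0.2 | 60% |
| 0.3 | 40% |
| 0.4 | 20% |
| 0.5 | 0% |

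**Midpoint.** An unchanged respondent at level x who ticks *Same as Before* is recorded with a shift of 4 − x. At level 2 this is +2 and at level 6 it is −2, each 2/6 = one third of the range, although nothing changed. On the first Day 1 occasion all 7 items (7 of 42 answers) offer this option with no earlier EMA to compare with. On later occasions *Before* could mean before the track, at the last survey or the previous day.

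**Sleep item.** It is repeated after the track on each of three days, when last night's sleep cannot have changed. That is 3 of 42 redundant answers.

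**The case against.** The strongest reply is that no planned result depends on the EMA. The confirmatory outcome is STAI-6 and section 8.2 names no EMA analysis. The link through the correlations is only a possibility: section 2 uses stress levels as a general term for the trial's main hypothesis, so STAI-6 may well be the intended measure. This stands, and it limits the weight of the point. It does not settle the matter, because section 5.3.2 describes STAI-6 as measuring anxiety symptoms and gives the EMA stress item the very purpose named in the correlations.

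Second, the labels do say good and bad, so many respondents may answer by valence throughout. The neuroticism scale is given only once, and 4 × 2 × 2 = 16 of the 24 exposed answers fall on Days 2 and 3. This is fair: the plan cannot show how often reversal would occur, and the attenuation table is conditional on an assumed q. But nothing in the plan secures the valence reading, and STAI-6 statements precede the EMA on every occasion.

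Third, direction could be partly checked afterwards against STAI-6 and the good-mood item, and the planned feedback on survey clarity might reveal confusion. Both are true. Neither can separate a 4 that means unchanged from a 4 that means neutral.

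Finally, repeating the sleep item is harmless, and naming the instrument for the correlations is a missing detail and not a fault of the scale. Both are minor additions to the main point.

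**Conclusion.** The point holds. The response format is wrong as written: four of seven items can be answered in opposite directions with no stated scoring rule, and the midpoint mixes change with level. The item count, the 24 of 42 answers exposed and the possible two-point midpoint shift follow directly from the text. The rate of reversal and the frequency of midpoint misuse are unknown, so any loss of sensitivity is illustrative.

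The consequence is limited. The confirmatory STAI-6 analysis is untouched, and the correlations are affected only if they use the EMA stress item. The change should still be made, because the midpoint ambiguity cannot be repaired after data collection and the scale could be carried into the larger study.

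**What to change.** Before the first participant:

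1. In section 5.3.2, replace the options for the six present-moment items with one intensity scale, for example 1 = *Not at all* to 7 = *Extremely*, and remove *Same as Before*. An agreement scale, as already used for the PARH, would also serve; the choice between the two is secondary.
2. State the direction of each item. On an intensity scale, higher means more of the named state: worse for fatigued, stressed, nervous and depressed, better for mentally sharp and good mood.
3. Ask the sleep item once a day, before the track, with anchors that fit it, such as the PARH disagree-to-agree format.
4. In section 8.2, say whether the stress measure in the correlations is STAI-6 or the EMA stress item.

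The cost is an edit of the Qualtrics labels, one scoring sentence in 5.3.2 and one phrase in 8.2. Each participant gives 42 − 3 = 39 EMA answers. The sample size, visit days and confirmatory model do not change.

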5. STUDY DESIGN, PROCEDURES AND METHODOLOGY

5.1 Study design

The research will adhere to a randomized, double-blind, 2-arm parallel-groups design. Participants will engage remotely from their home. The entire study duration is set at 3 days.

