Participants will then be randomly assigned by the Qualtrics engine to either the experimental group, which listens to a mindfulness audio track, or the control group, which listens to a 'sham meditation' track. Both tracks are embedded within the Qualtrics survey. Participants cannot skip this portion of the survey for 10 minutes, ensuring they listen to the entire 10-minute audio track. Afterward, participants will be asked to sit quietly for three minutes without engaging in any activities. This pause is necessary because, some of the audio track encompasses the application of mindfulness principles while performing a routine activity (e.g., brushing teeth) during the listening of a mindfulness track. Although the movement involved in this activity is minimal, we want participants to sit still for three minutes to avoid introducing any confounding variables in the subsequent HRV assessments. The survey will be programmed to remain stuck during this period to prevent participants from skipping this step.

Following the quiet period, participants will complete post-intervention assessments for STAI-6, EMA and HRV. Participants will be thanked and instructed to reopen the survey link the following day, ideally at the same time between 9am and 9pm. On Day 2, they will complete the same pre-intervention assessments (STAI-6, EMA and HRV), listen to a different audio track, either mindfulness or sham meditation, depending on their group allocation, sit for three minutes, and then complete the post-intervention assessments mirroring Day 1. On Day 3, participants will undergo the same procedure as Day 2 but will listen to another audio track (mindfulness or sham). Additionally, they will complete the FFMQ, answer questions about their expectations of the intervention, its credibility, the PARH scale, and the usability questionnaire. Finally, participants will be thanked for their participation in the study and debriefed.

6. Ethics information

This study will be conducted in accordance with the ethical principles outlined in the Declaration of Helsinki and in compliance with applicable regulatory requirements. The final study protocol, along with the latest version of the Participant Information and Consent Form, will receive written approval from the A*STAR Institutional Review Board (A*STAR IRB) before any participants are enrolled.

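### The effectiveness item tells both arms they had meditation training and is listed ahead of the arm guess, so it can lead that guess; neutral wording would remove the cue

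*Combined protocol and SAP*

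**What the plan says.** Section 5.3.2, in its end-of-trial part on expectancy and credibility, describes one effectiveness item, given "during the final phase of post-intervention testing" and rated 0 to 10: "How effective do you believe the meditation training has been in alleviating stress". There is a single wording, with no version for the sham arm.

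The next item listed is the arm guess: "If you were informed that you might have received either meditation training or control training, which type do you believe you received". The two answers are Meditation and Control, with no 'don't know' option, and a 0 to 10 confidence rating follows.

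Section 5.4 gives the same relative order for Day 3, when participants "answer questions about their expectations of the intervention, its credibility, the PARH scale, and the usability questionnaire". Neither section mentions neutral wording or randomised item order.

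Section 8.2 lists, among the exploratory analyses, an analysis of the responses on credibility and on awareness of the hypothesis "to assess equal credibility of the intervention for the mindfulness condition and the sham". It names no index, test or threshold. Section 5.1 describes a "randomized, double-blind, 2-arm parallel-groups design", and section 5.2.2 says the sham relies on "terminology designed to create the expectation of authentic mindfulness meditation for those unfamiliar with the practice".

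**The concern.** The effectiveness item presupposes that the respondent had meditation training. The guess item that follows is only hypothetical, and one of its two options repeats the same phrase. To answer 'Control', a participant must contradict the premise of a question just answered. That makes the first item a leading cue for the second.

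Section 1 says the sham is there to separate a genuine effect from a demand effect, as groundwork for a multi-site trial. Whether newcomers can tell the sham from mindfulness is thus one of the main things the pilot should find out. The arm guess is the only item that asks this directly. If the questionnaire itself prompts the answer, the data cannot separate a credible sham from a leading question.

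**Working it through.** **Step 1: the text.** The documents state no guess rate, blinding index or threshold, so there is no plan figure to reproduce. The label applies to both arms, the guess follows it in 5.3.2, and 5.4 agrees on that order.

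**Step 2: direction, with assumed rates.** Let pM and pS be the shares who would answer 'Meditation' without the cue in the mindfulness and sham arms. Suppose the cue converts a share L of would-be 'Control' answers in each arm:

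p′ = p + L(1 − p), so the gap becomes pM′ − pS′ = (1 − L)(pM − pS).

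The Bang blinding index is 1 − 2pS′ in the sham arm and 2pM′ − 1 in the mindfulness arm. With assumed pM = 80% and pS = 40%:

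| L | Mindfulness | Sham | Gap (points) | Sham index | Mindfulness index |
|---|---|---|---|---|---|
| 0 | 80% | 40% | 40 | +0.20 | +0.60 |
| 0.1 | 82% | 46% | 36 | +0.08 | +0.64 |
| 0.3 | 86% | 58% | 28 | −0.16 | +0.72 |
| 0.5 | 90% | 70% | 20 | −0.40 | +0.80 |

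For L = 0.3: 0.80 + 0.3 × 0.20 = 0.86 and 0.40 + 0.3 × 0.60 = 0.58.

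**Step 3: does the direction depend on the model?** With a separate share for each arm, the gap changes by L_M(1 − pM) − L_S(1 − pS). At 80% and 40% this is 0.20 L_M − 0.60 L_S, so the gap narrows unless the cue converts more than three times as large a share in the mindfulness arm as in the sham arm.

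A constant shift s on the logit scale, logit p′ = logit p + s, gives:

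| Start | s | Gap (points) | Sham index |
|---|---|---|---|
| 80% / 40% | 0 | 40 | +0.20 |
| 80% / 40% | 0.5 | 34.5 | −0.05 |
| 80% / 40% | 1.0 | 27.1 | −0.29 |
| 40% / 20% | 0 | 20 | +0.60 |
| 40% / 20% | 0.5 | 23.2 | +0.42 |
| 40% / 20% | 1.0 | 24.0 | +0.19 |

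When both starting rates are low, the gap widens a little. The sham index falls in every row where a cue is applied.

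**Step 4: precision.** Section 8.1 targets at least 50 participants after dropout. The allocation ratio is not stated; assume 25 per arm. The standard error of an 80% versus 40% gap is √[(0.80 × 0.20 + 0.40 × 0.60)/25] = √0.016 = 0.126, a 95% interval of about ±25 points (1.96 × 0.126). The 12-point distortion at L = 0.3 is smaller than this. It is a bias, however, and more participants would not remove it.

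**The case against.** The strongest reply is that the phrase adds little. Both arms hear meditation framing for three days by design, so one more use of the word continues the cover story. The participant information is not in the text available for review, so the item's separate effect cannot be isolated. This stands, and it limits the likely size. It does not defend the wording: belief created by the sham is what the guess should measure, whereas belief prompted by the questionnaire is an artefact of measurement.

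The order is also inferred from prose. Section 5.3.2 describes usability and the hypothesis-awareness scale before expectancy and credibility, while 5.4 lists them after, so neither list is clearly a fixed survey sequence. Both nevertheless put effectiveness ahead of the guess, and neutral wording works in any order.

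A reader might infer three stronger things that the documents do not support:

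- **That the blind will certainly look better than it is.** The sham-arm guess would look more favourable if the cue works. The gap can widen at low starting rates, and a mindfulness-arm index would look worse.
- **That the guess is the only evidence on credibility.** Section 8.2 also uses the hypothesis-awareness scale. The confidence rating, the effectiveness rating and the usability questions on perceived efficacy can all be compared between arms.
- **That the guess should be asked first.** This would reveal a possible control before effectiveness is rated and could lower the ratings of sham participants who suspect they had it. Effectiveness first is a defensible order.

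**Conclusion.** The point holds as a wording fault in an exploratory but important check. Both arms are told that they had meditation training, and the arm guess listed next reuses that phrase as an answer option. If the cue has any effect, it raises the share of sham participants answering 'Meditation', and in many plausible scenarios it narrows the between-arm gap.

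The size is unknown and may be small. The illustrated narrowing, from 40 to 28 points at L = 0.3, rests entirely on assumed rates, an assumed conversion share and an assumed model. A reader might go further and conclude that the pilot would pass a recognisable sham on to the multi-site trial. The plan sets no decision rule on guess rates, so that does not follow. The confirmatory STAI-6 analysis does not use these items. The change is worth making because it costs almost nothing and protects the one direct question about arm.

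**What to change.** In the effectiveness item, replace the reference to meditation training with an arm-neutral term used identically in both arms, for example 'the audio sessions you listened to'. Use the same term in any survey question shown before the guess, including the usability questions if the built survey places them earlier. Keep effectiveness before the guess, and state the final Day 3 item order in the protocol so that 5.3.2 and 5.4 agree.

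The cost is a few words in the survey and a slight further departure from the source questionnaire, which the plan already describes as adapted.
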